4.3. Safety Population

The Safety Population includes all randomized subjects who receive any amount of investigational product (OCA or placebo). The Safety Population will be the primary population used for safety analyses and treatment assignment will be based on the treatment actually received.

4.4. Pharmacokinetic (PK) Population

The PK Population includes all OCA subjects who have at least one confirmed fasted analyzable sample. Subjects must have been fasting for approximately 8 hours prior to the visit and must not have any major protocol deviations that potentially affect exposure levels. The PK Population will be used for OCA PK analyses.

5. SUBJECT DISPOSITION

Subject disposition will be tabulated by treatment group and overall and will include the number and proportion of subjects screened and enrolled, as well as subject discontinuation status and reasons for discontinuing treatment or study. Discontinuation status will be additionally presented for subjects with and without a primary endpoint event. Subject disposition will be summarized for all analysis populations defined in [Section 4](#).

Subjects are considered to have discontinued from the study if they discontinued study visits and did not consent to follow-up contact or medical record review, or if they withdrew consent for follow-up contact or medical record review. Subjects are considered to have started commercial Ocaliva if they discontinued treatment or study visits due to initiating commercial Ocaliva, or if Ocaliva is recorded as a concomitant medication.

5.1. Protocol Deviations

The Investigator is not permitted to deviate from the protocol in any significant way without proper notification to the Sponsor (or designee). Only the Sponsor may amend the protocol. Any change in study conduct considered necessary by the Investigator will be made only after consultation with the Sponsor, who will then issue a formal protocol amendment to implement the change and obtain regulatory approval. The only exception is when the Investigator considers a subject's safety to be compromised if immediate action is not taken.

Protocol deviations identified during the conduct of the study will be summarized and listed.

6. DEMOGRAPHICS AND BASELINE DISEASE CHARACTERISTICS

Demographic variables (eg, age at informed consent, age categorized as < 65 years and \geq 65 years and by decades, sex, race, ethnicity, and geographic region), other baseline characteristics (eg, weight, height, body mass index, BMI categorized as < 30 kg/m² and \geq 30 kg/m², use of UDCA at screening (Yes/No)), and key liver function test results at baseline (eg, ALP, total

bilirubin, albumin, platelets, international normalized ratio (INR), GGT, creatinine) will be summarized and presented by treatment and overall for each analysis population.

Summaries of PBC disease characteristics will use data collected from the PBC Disease History electronic case report form (eCRF). Variables from the PBC Disease History eCRF include the following:

- Age at PBC diagnosis
- Duration of PBC in years at time of informed consent
- PBC stage of most recent liver biopsy
- History of PBC related pruritus (Yes/No)
- Severity of most recent pruritus event
 - Ongoing at screening
- History of PBC-related fatigue (Yes/No)
 - Ongoing at screening
- Overall severity of PBC-related fatigue
- Use of UDCA (Never/Previous/Current)
- Duration of previous/current UDCA use in years at time of informed consent

For categorical variables, the number and percentage of subjects within each category, including a category for missing data, will be presented. For continuous variables, summary statistics will include the number of subjects and the mean, standard deviation (SD), standard error of the mean (SEM), median, 25th and 75th quartiles, minimum, and maximum values.

No inferential statistical comparisons will be performed.

7. PRIOR THERAPY AND MEDICAL HISTORY

Prior therapy and medical history includes any therapy or diseases that occurred or any medication taken prior to baseline date.

Prior therapy will be mapped to Anatomic Therapeutic Chemical (ATC) class and preferred term (PT) using WHO Drug Dictionary version Global B3, March 2020 (or later version) and summarized by ATC class, preferred term, and treatment in the Safety Population. Summaries will be ordered by descending order of incidence of ATC class and preferred term within each ATC class.

Medical history will be mapped to PTs and system organ classes (SOCs) using MedDRA dictionary version 23.1 (or later version) and summarized by SOC, PT, and treatment group in the Safety Population. Summaries will be ordered by descending order of incidence of SOC and preferred term within each SOC.

8. EFFICACY ANALYSES

The efficacy endpoints and the planned analyses of these endpoints are described below.

8.1. Primary Efficacy Endpoint

The following table identifies the elements of the intercurrent events and strategies to address for primary efficacy endpoint.

Primary Estimand	
Population	Adult subjects with PBC who are at higher risk of liver-related clinical complications.
Endpoint (variable)	
Compare the effect of OCA to placebo, in conjunction with established local standard of care, on the composite clinical outcomes as measured by time from randomization to the first occurrence of the following post-randomization events:
 
Group 1 (applies to all subjects):
 
 • Death (all-cause) • Liver transplant • Hospitalization (as defined by a stay of 24 hours or greater) for new onset or recurrence of: 
 – Variceal bleed – Hepatic encephalopathy (as defined by a West Haven score of ≥ 2) – Spontaneous bacterial peritonitis (confirmed by diagnostic paracentesis OR presence of $>250/\text{mm}^3$ PMNs in the ascitic fluid) – Bacterial empyema (confirmed by diagnostic thoracentesis OR presence of $>250/\text{mm}^3$ PMNs in the pleural fluid) • Uncontrolled or refractory ascites (requiring large volume paracentesis) • Portal hypertension syndromes (hepatorenal, portopulmonary, and hepatopulmonary) • MELD-Na score ≥ 15 (for subjects with baseline MELD-Na score < 12) • MELD score ≥ 15 (for subjects with baseline MELD-Na score ≥ 12) 
Group 2 (applies to subjects without decompensation at baseline):
 
 • Progression to decompensated liver disease (for subjects without decompensation at baseline). See Section 2.1.1 Group 2 and Section 8.1.1 for prioritization list and analysis. 
Group 3 (applies to subjects without decompensation or clinical evidence of portal hypertension at baseline):
 
 • Progression to clinical evidence of portal hypertension without decompensation (for subjects without decompensation or clinical evidence of portal hypertension at baseline). See Section 2.1.1 Group 3 and Section 8.1.1 for prioritization list and analysis.

Primary Estimand		
Intercurrent events/ Strategies to address	Use of commercial OCA as concomitant medication or IP/study visit discontinuation due to commercial OCA use	Treatment policy will use for primary analysis: Treatment effect regardless of intercurrent event.

8.1.1. Primary Analyses

The primary efficacy analyses will compare OCA to placebo with respect to the primary efficacy endpoint using the ITT Population. Only adjudicated events will be included in the analysis. The number and percent of subjects censored and with events will be presented. Descriptive statistics will be presented for the time-to-event endpoints.

If a subject experiences more than one event in the composite primary endpoint (all Group 1 – Group 3 events), only the event that occurs first will be included in the analysis. Subjects with no data after randomization will be censored on Day 1 (first day of IP dosing). Subjects who do not experience an event will be censored at the time of their last contact. Last contact is the date of discontinuation from regularly-scheduled study visits for subjects who did not consent to follow-up and the date of discontinuation from contact visits (medical record review / semi-annual phone calls) for patients who consented to follow-up. The total number of patient years observed, patient years and percentage of patient time accrued after discontinuation of IP, and

patient years and percentage of patient time accrued after initiation of commercial OCALIVA will be presented overall and by treatment group.

The 2 treatment groups will be compared using the log rank test stratified by the randomization stratification factors, conducted at the 2-sided alpha level of significance described in [Section 8.6](#). Kaplan-Meier (KM) estimates of the distribution of the time-to-event will be tabulated and graphed by treatment group. The tabulation will include the KM estimate of the 25th, 50th (median), and 75th percentiles and corresponding 2-sided 95% CIs, where the percentiles can be estimated. KM tabulations will present time to event in days; KM graphs will present time to event in months. The hazard ratio and 95% CI will be determined based on a Cox regression model stratified by randomization strata to estimate the magnitude of the effect. The proportionality of hazards will be assessed using Schoenfeld residuals.

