3.2. Sample Size Determination

The following assumptions were used in the Protocol Version 6 sample size calculations:

- Exponential survival curves, placebo survival estimate of 0.6 at 8 years with a hazard ratio of 0.60, and total study duration of 10 years (from first subject enrolled), allowing for 4 years of subject accrual and 6 years of follow up.
- Subjects will be randomized in a 1:1 ratio to placebo or OCA.
- The 2 treatment groups will be compared using a 2-sided log rank test at the 5% level of significance.
- Two interim analyses and one final analysis are planned, with interim analyses occurring after the accrual of 50% and 75% of clinical outcome events, respectively.
- A dropout rate of 10% is assumed

Based on the randomization ratio, significance level, and assumed hazard ratio, a total of 127 events (both groups combined) was to provide 80% power to demonstrate a statistically significant difference between OCA and placebo on time to liver-related outcomes, including all-cause mortality.

In addition, based on the remaining assumptions stated above, it was estimated that approximately 428 subjects would be enrolled to attain 127 events.

Sample size calculations were based on the following composite endpoint: time to first occurrence of death, liver transplant, MELD ≥ 15 , uncontrolled ascites, or hospitalization for new onset or recurrence of variceal bleed, hepatic encephalopathy, or spontaneous bacterial peritonitis.

Due to enrollment challenges and difficulties to keep patients in the study, the trial will be terminated early by sponsor. To better evaluate the benefit-risk ratio, the composite endpoint will be revised to include additional components that occur earlier in the progression of PBC

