8.6. Multiple Comparisons/Multiplicity

An interim analysis was conducted after 80 events were observed. A group sequential design using the O'Brien-Fleming type alpha-spending function ([Lan 1983](#), [Reboussin 2000](#)) was used to control the overall two-sided 0.05 significance level that is at an information fraction of 0.63 of the total of 127 events, corresponding to an alpha spend of 0.009. The primary analysis will be conducted at 2-sided 0.041 significance level. No interim analysis will be performed based on the updated endpoints and methodology. The primary endpoint analysis for European Medicines Agency (EMA) filing will be conducted at 2-sided 0.041 significance level.

For the final analysis, the hypothesis testing of key secondary analyses will compare placebo and OCA (the key secondary endpoints are stated in [Section 8.2](#)), provided that the primary efficacy endpoint comparison is statistically significant in favor of OCA. If the primary comparison is not statistically significant then comparison of the key secondary endpoints will be considered as supportive or supplemental. If the primary comparison is statistically significant, the key secondary endpoints will be tested hierarchically in the order described in [Section 8.2](#) at a 2-sided 0.041 significance level. All other secondary endpoints will be tested at nominal 0.041 alpha level.

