14. DEVIATIONS FROM PROTOCOL

14.1. Primary Efficacy Endpoint and Analysis

Due in part to high discontinuation rates and requests from sites to close, the decision was made to stop 747-302 early, at approximately 67% information (84 adjudicated Protocol Version 6 endpoints observed). To increase the number of endpoint events and power to detect a difference, the primary efficacy endpoint has been expanded to include:

- Portal hypertension syndromes (hepatorenal, portopulmonary, or hepatopulmonary)
- Progression to decompensated liver disease (for subjects without decompensation at baseline)
- Progression to clinical evidence of portal hypertension without decompensation (for subjects without decompensation or clinical evidence of portal hypertension at baseline).

The primary efficacy analysis remains the stratified log rank test. With the inclusion of additional endpoints that occur earlier in the course of the disease, the log rank test is limited to each subject's first event, which is likely to be an outcome of lesser clinical importance. A win ratio analysis was added as a sensitivity analysis, to allow for a hierarchical comparison of the composite endpoints. The win ratio analysis allows for the comparison of more severe events such as death and liver transplant to be prioritized over the comparison of earlier-stage events such as progression to clinical evidence of portal hypertension.

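### The primary test and hazard ratio use only UDCA and a bilirubin split; adjusting for baseline MELD-Na would probably gain power, by an amount the documents do not settle

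*SAP*

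**What the plan says.** Section 8.1.1 compares the arms by a log-rank test stratified on the randomisation factors, which Section 3.1 gives as UDCA use and bilirubin above or not above ULN. The hazard ratio is "determined based on a Cox regression model stratified by randomization strata to estimate the magnitude of the effect". Section 8.6 sets the level: "The primary analysis will be conducted at 2-sided 0.041 significance level". The estimand table in Section 8.1 names the log-rank test as the population-level summary. None of the seven sensitivity analyses in Section 8.1.2 fits an outcome model adjusted for baseline severity.

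Baseline severity appears elsewhere in the plan:
- In the Section 8.1 endpoint, the MELD-type component is defined separately "for subjects with baseline MELD-Na score" below 12 and at or above 12. The added components are restricted by stage: "Group 2 (applies to subjects without decompensation at baseline", with a narrower restriction for Group 3.
- Section 8.7 defines baseline disease stage for subgroups, and Appendix A gives the MELD-Na formula.
- Appendix A lists continuous bilirubin, albumin, platelets and other baseline values as predictors of both censoring and outcome, but only for the IPCW weights.

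Section 14.1 gives the motive for the wider endpoint: "To increase the number of endpoint events and power to detect a difference, the primary efficacy endpoint has been expanded".

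**The concern.** A single cut at ULN leaves a wide spread of risk inside a stratum. Section 3 admits bilirubin up to 5 times ULN, and all of that range above ULN falls on one side of the cut. With the Appendix A coefficient, the range spans 3.78 × ln 5 = 6.1 MELD points, assuming ULN is at least 1.0 mg/dL, against an event threshold of 15.

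When an omitted covariate is strongly prognostic, the strata-only hazard ratio lies closer to 1 than the conditional one and the log-rank test loses power. The sponsor accepted components that Section 14.1 concedes are of lesser clinical importance in order to gain power. Covariate adjustment could recover some power without adding such events. It would also correct for chance imbalance in severity among about 334 subjects (Clinical Pharmacology Analysis Plan, Section 5).

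**Working it through.** **1. The plan's own figures.** Section 3.2 assumes "placebo survival estimate of 0.6 at 8 years with a hazard ratio of 0.60" and states "The 2 treatment groups will be compared using a 2-sided log rank test at the 5% level of significance". On that basis "a total of 127 events (both groups combined) was to provide 80% power".
- Freedman: d = (1.960 + 0.842)² × (1.6/0.4)² = 7.85 × 16 = 126, against 127 stated. Power at 127 events = Φ(√127 × 0.25 − 1.960) = 80.4%. (Schoenfeld gives 121 events.)
- Subjects: exponential survival with 4 years' uniform accrual and 6 to 10 years' follow-up gives a mean event probability of 0.331. Then 127/0.331 = 384, and 384/0.9 = 427, against 428 stated.

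**2. Final level.** At two-sided 0.041 and HR 0.60, Freedman power is Φ(√84 × 0.25 − 2.044) = 59.8% at 84 events and Φ(√127 × 0.25 − 2.044) = 78.0% at 127. The 84 is the number of Protocol Version 6 events in Section 14.1. No count is given for the expanded endpoint, so 84, 127 and 167 serve as reference points. Carrying HR 0.60 over to the expanded endpoint is also an assumption.

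**3. Gain from adjustment, conditional HR 0.60.** Simulation with N = 334, 1:1 allocation, two-sided 0.041 and 1,500 trials per cell (Monte Carlo error about 1 point). The log-rank test stratified by UDCA and bilirubin is compared with the arm test from a stratified Cox model that includes the severity score. The SD of the score's log-hazard within strata is assumed.

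| SD (HR per SD) | 84 events | 127 events | 167 events |
|---|---|---|---|
| 0.3 (1.35) | +1.0 | +1.1 | +1.2 |
| 0.5 (1.65) | 55.9% to 58.9%, +2.9 | 72.3% to 77.7%, +5.5 | +7.2 |
| 0.75 (2.12) | 50.8% to 57.1%, +6.3 | 66.8% to 78.5%, +11.7 | +14.1 |
| 1.0 (2.72) | 46.9% to 58.9%, +12.0 | 61.0% to 77.5%, +16.5 | +20.7 |
| 1.25 (3.49) | +17.1 | +28.1 | +30.1 |

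Gains are rounded from unrounded power. A second simulation (bilirubin HR 3, half the subjects above ULN, 2,000 trials) gives 73% to 78%, 68% to 80% and 60% to 77% at 127 events for SD 0.5, 0.75 and 1.0. These are gains of 5, 12 and 17 points.

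**4. If 0.60 is the strata-only HR.** The conditional HR is then stronger, for example 0.589 (SD 0.5, 84 events) or 0.531 (SD 1.0, 127 events). Gains for SD 0.5, 0.75 and 1.0 are:
- 84 events: 2.6, 6.5 and 13.0 points
- 127 events: 5.9, 7.9 and 12.1 points
- 167 events: 4.9, 8.9 and 11.1 points

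**5. Stage as the covariate.** Three stages (none / portal hypertension / decompensated, in assumed shares of 50/30/20%), with Group 1 risk rising by stage and Group 2 and 3 events closed to later stages. Over 84 to 167 events:

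| Total hazard by stage | Gain (points) |
|---|---|
| 4 : 4 : 5 (effects offset) | −1.0 to −0.1 |
| 4 : 4.5 : 8 | 0.5 to 1.9 |
| 2.5 : 6 : 14 | 7.5 to 11.9 |

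**The case against.** The stratified log-rank test is valid, controls type I error and matches the design test, and Section 14.1 keeps it deliberately. A reader might infer that the plan's hazard ratio is biased towards 1. It is not: the strata-only and conditional hazard ratios are different quantities, and the gap between them is non-collapsibility. This part of the objection stands in full.

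The size of the gain is assumed. The severity score in steps 3 and 4 is normal and is fitted by the model that generated it, which favours adjustment. Appendix A sets laboratory values below 1.0 to 1.0 and caps sodium at 137, so MELD-Na may cluster near its floor when bilirubin is not above ULN. Bilirubin is also already a stratum. This stands, and is why SD 0.3 is shown.

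A reader might infer that, because baseline stage and MELD-Na decide which events can count, they must predict time to first event. The documents do not support that step. Decompensated subjects lose Group 2 and 3 events while carrying more Group 1 risk. By the Appendix A formulas MELD-Na is at least MELD whenever MELD is below 40, so subjects entering at MELD-Na 12 or more face the stricter MELD criterion. The case for MELD-Na therefore rests on expected prognostic value, not on the eligibility rules.

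A reader might also infer that the trial stopped for lack of events. Sections 3.2 and 14.1 cite enrolment, retention, discontinuations and site closure requests; the event shortfall was the result.

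Finally, adjustment has a price. The Cox hazard ratio becomes conditional, and the test changes after an interim look at the Protocol Version 6 endpoint. Neither makes adjustment invalid. In the scenarios run, the worst power loss was about 1 point.

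**Conclusion.** The point holds as one of efficiency. The primary analysis leaves out a severity measure that the SAP already derives, in a trial whose endpoint was widened to gain power.

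With a within-stratum log-hazard SD of 0.5 to 1.0, the gain is about 3 to 12 points at 84 events and 5 to 17 at 127 (conditional HR 0.60), or about 3 to 13 points if 0.60 is the strata-only HR. With SD 0.3 it is about 1 point. These figures depend on the assumed SD, event count and hazard ratio. A reader should not take any of them as a power loss shown by the documents. The change is worth making but is not needed for validity.

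**What to change.** Before unblinding, specify in Section 8.1.1 that the primary comparison is adjusted for continuous baseline MELD-Na within the randomisation strata, by one of two named methods:
- a covariate-adjusted stratified log-rank test, which keeps the log-rank summary in the Section 8.1 estimand table; or
- the arm test from the stratified Cox model with MELD-Na, with that table amended to match.

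Label the adjusted hazard ratio as conditional on baseline MELD-Na. Report the present stratified log-rank and Cox results alongside as the unadjusted analysis. Use baseline disease stage only as a further stratum or in a supportive model, because event eligibility differs by stage and proportional hazards across stages is doubtful.

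Record the change in Section 14.1. Section 8.2.1 takes its method from Section 8.1.1, so state whether the adjustment also applies to the key secondary endpoints, including the one that is primary for the EMA filing.

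The cost is SAP wording and programming; no new data are needed. The downsides are a hazard ratio conditional on baseline severity, a test that depends modestly on the covariate model, and one more late change to the primary analysis after an interim look.

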8.1.2. Sensitivity Analyses

The following sensitivity analyses will be carried out on the primary endpoint, with different population, strategy to handle the intercurrent events, or summary.

No.	Population	Strategies to address intercurrent events	Population-level summary
1	Subset of primary population, who had no major protocol violations.	Same as primary analysis	Same as primary analysis
2	Same as primary analysis	Same as primary analysis	The 2 treatment groups will be compared using the win ratio (Pocock 2012) using the unmatched method within the bilirubin randomization strata. The 95% confidence interval will be calculated using a bootstrapping method and a p-value will be calculated using the stratified Finkelstein-Schoenfeld test (Finkelstein 1999).
3	Same as primary analysis	Data collected after the intercurrent events to be excluded (while on treatment policy)	For subjects who didn't experience an event before the intercurrent event, multiple imputation will be carried out for time to event based on the available data after the intercurrent event. Details is included in the appendix.
4	Same as primary analysis	Exclude data after 90 days after a patient discontinues IP.	Same as primary analysis.
5	Same as primary analysis	Include only data prior to when a patient starts commercial OCALIVA.	Same as primary analysis.
6	Same as primary analysis	Include only data prior to when OCA was commercially available in the subject's country.	Same as primary analysis.
7	Same as primary analysis	Hypothetical strategy, ie, as if the intercurrent events didn't happen.	Hazard ratio and 95% CI will be estimated using a weighted Cox regression model with Sandwich estimator. The derivation of the weights based on Inverse Probability of Censoring Weighting (IPCW) is detailed in the appendix.

